### **Potential risks and risk management of neridronic acid**

#### *Acute phase reaction*

The most common side effects associated with parenteral administration of aminobisphosphonates are flu-like symptoms, commonly referred to as "acute phase reaction" (Reid et al. 2010; Silverman et al. 2011). Symptoms include fever, myalgia, fatigue, headache, diarrhea, arthralgia, and bone pain. These are self-limiting and usually resolve after 24 hours to 48 hours. Symptoms of the acute phase reaction typically occur following the first administration and are absent or decreased following subsequent administrations. For symptomatic management of the acute phase reaction, oral acetaminophen (paracetamol) is recommended (for details, see Section 1.4.2). Non-steroidal anti-inflammatory drugs should not be used to alleviate the symptoms of the acute phase reaction due to their potential to cause acute changes in renal function, which may confound renal safety assessments.

#### *Ocular effects*

Eye disorders have been reported with neridronic acid and appear to be associated with the acute phase reaction. These events include anterior uveitis, episcleritis, conjunctivitis and ocular pain. As severe ocular inflammation may increase the potential risk of long-term vision loss, treatment with neridronic acid will be discontinued at first signs of ocular inflammation, followed by an ophthalmologic exam.

#### *Hypocalcemia*

Aminobisphosphonates are potent inhibitors of bone turnover, and are thus associated with a risk of hypocalcemia.

The normal compensatory mechanism is an increase in parathyroid hormone, which can trigger renal absorption of calcium and vitamin D3 production in response to a decreased calcium efflux from the skeleton after bisphosphonate therapy (Polyzos et al. 2011).

Subjects with abnormal blood calcium or magnesium concentrations, a history of disorders that impair the compensatory increase in parathyroid hormone, or concomitant use of any drug with

known potential to cause hypocalcemia will be excluded from the trial. Retesting of out-of-range values is permitted once during the Enrollment Period. Albumin-corrected serum calcium should be considered when serum albumin is below the normal range (e.g., <3.5 g/dL).

All subjects will be provided with supplemental calcium and vitamin D, starting from Visit 1 and continuing through to the end of the trial (for details, see Section 1.4.2). Subjects with vitamin D levels below 30 ng/mL (75 nmol/L) will receive supplementation to achieve values of at least 30 ng/mL (75 nmol/L) prior to allocation to IMP. Subjects who do not reach vitamin D levels of at least 30 ng/mL (75 nmol/L) following appropriate supplementation will be excluded from the trial.

#### *Renal toxicity*

Based on the available data for neridronic acid, there is no clinical evidence for renal safety concerns to date. Nevertheless, renal toxicity was observed in non-clinical studies of neridronic acid and is regarded as a class effect of intravenous bisphosphonates. In most cases, signs for renal toxicity following administration of other intravenous bisphosphonates were transient and reversible after discontinuation of the drug or dose adjustment. Pronounced renal toxicity is a rare event, more common in long-term use, and there is a contributing role of pre-existing renal disease as well as other factors like other medication associated with renal toxicity and dehydration.

Bisphosphonates are rapidly cleared by the kidneys, potentially leading to a high concentration in kidney tissue during and immediately after the infusion. Dose and infusion time are the main factors related to renal toxicity.

In order to mitigate the risk of renal toxicity, subjects with evidence of severe renal impairment will be excluded (for details, see exclusion criterion 1).

Taking into account that renal toxicity due to intravenous bisphosphonates is related to the maximum drug concentration achieved and not the area under the curve of drug exposure (Khosla et al. 2012), 400 mg neridronic acid will be administered as 4 infusions of 100 mg neridronic acid administered over 240 minutes at Visit 2, Visit 3, Visit 4, and Visit 5 (and Visit 11, Visit 12, Visit 13, and Visit 14 during Treatment Period B) to subjects with no or mild renal impairment.

For subjects with moderate renal impairment, the dose will be adjusted (see Section 10.2).

Due to the potential for renal toxicity with neridronic acid as with other bisphosphonates, renal safety monitoring will be implemented in this trial together with defined stopping criteria (for details, see Section 9.3.2).

#### *Cardiovascular*

Despite the ability to transiently lower calcium levels, there has been no indication to date that bisphosphonates, as a class, cause prolongation of QT interval. Neridronic acid has not been studied in dedicated safety trials to evaluate a potential effect on the QT interval. Subjects with risk factors for QT prolongation or cardiac arrhythmia, including abnormal serum potassium levels, are excluded from this trial. Subjects will undergo regular 12-lead ECG examinations throughout the trial.

#### *Medication-related osteonecrosis of the jaw*

Osteonecrosis of the jaw is a rare adverse effect of bisphosphonate therapy, most commonly reported for patients with multiple myeloma and osteolytic bone metastases receiving repeated

monthly infusions for treatment of skeletal related events and bone pain. Factors that may contribute to risk of osteonecrosis of the jaw include recent tooth extraction, unhealed or infected extraction sites, dental/periodontal disease, improperly fitting dentures causing injury, and prior radiation of the head or neck.

Invasive dental procedures should be avoided during the trial; however, subjects who require emergency dental surgery during the trial should proceed with appropriate treatment including prophylactic antibiotics and frequent follow-up. Subjects should be encouraged to use good dental hygiene (daily flossing and gentle brushing) throughout the trial.

#### *Osteonecrosis of the external auditory canal*

Osteonecrosis of the external auditory canal has been reported with bisphosphonates, mainly in association with long-term therapy. Possible risk factors for osteonecrosis of the external auditory canal include steroid use and chemotherapy and/or local risk factors such as infection or trauma. The possibility of osteonecrosis of the external auditory canal should be considered in patients receiving bisphosphonates who present with ear symptoms including chronic ear infections and/or local risk factors such as infection or trauma.

#### *Atypical femoral fractures*

Although a causal relationship has not been conclusively established, meta-analysis suggests there is an increased risk of atypical femoral fractures in long-term bisphosphonate users. These fractures have a low prevalence (1.1% of all femoral fractures), and the absolute risk to patients receiving bisphosphonates is low. Subjects should be advised to report any thigh, hip, or groin pain, and any patient who develops these symptoms should be evaluated for the presence of an incomplete femur fracture.

#### *Other effects on bone*

Although the potential for deleterious effects on bone following long-term treatment with bisphosphonates remains controversial to this day, no histomorphometric evidence of osteomalacia was reported at doses up to neridronic acid 250 mg in patients with Paget's disease of bone (McCloskey et al. 1987; Atkins et al. 1987), in contrast to findings following administration of the first generation bisphosphonate, etidronic acid.

Supporting the absence of any important effect on bone health, long-term neridronic acid treatment increased bone mineral density and lowered risk of clinical fracture in children and adults with osteogenesis imperfecta. These results argue against a deleterious effect on bone mineralization due to neridronic acid.

However, the potential for deleterious effects of bisphosphonates on bone has been suggested in conditions of low bone turnover, such as renal osteodystrophy or other adynamic bone disease, although the benefit/risk profile in these conditions is unclear. In addition to exclusion of subjects with chronic kidney disease stage 4 and 5, subjects with known defects in bone mineralization or adynamic bone disease are excluded from the trial.

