### **1.3.2 Exclusion criteria**

Subjects will not be eligible for the trial if any of the following exclusion criteria apply. Subjects will only receive IMP if documentation is available showing that they do not meet any of these exclusion criteria.

1. Evidence of severe renal impairment (estimated glomerular filtration rate [eGFR] less than 30 mL/min/1.73 m^2 using the 2009 Chronic Kidney Disease Epidemiology Collaboration [CKD-EPI] creatinine equation [Levey et al. 2009] or a urinary albumin to creatinine ratio [ACR] greater than 150 mg/g), based on central safety laboratory data obtained prior to Visit 2. Note: a single repeat laboratory test is allowed.
2. Serum calcium or magnesium outside of the central laboratory's reference range, based on central safety laboratory data obtained prior to Visit 2 (2 repeat laboratory tests are allowed); a history of hypocalcemia or a metabolic disorder anticipated to increase risk for hypocalcemia (e.g., hypoparathyroidism); anticipated need for any new drug with known potential to cause hypocalcemia (e.g., aminoglycosides, new treatment with or dose adjustment of loop diuretics) during the trial.  
Subjects on a stable dose of loop diuretics may receive treatment with IMP as long as no dosage increases in the diuretic medication are anticipated and calcium levels are in the reference range.
3. Vitamin D deficiency, defined as a 25(OH)D level less than 30 ng/mL (75 nmol/L), based on central safety laboratory data obtained prior to Visit 2 (up to 4 repeat laboratory tests are allowed). Subjects with vitamin D deficiency should receive appropriate supplementation during the Enrollment Period. A vitamin D level of at least 30 ng/mL (75 nmol/L) must be documented prior to allocation to IMP.

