11. History of malignancy within 2 years prior to Visit 1, with the exception of basal cell carcinoma.
12. Use of nerve blocks, ketamine infusions, intravenous immunoglobulin, acupuncture, electromagnetic field treatment, or initiation/implementation of radiofrequency ablation or other sympathectomy procedures, or peripheral nerve stimulation within 6 weeks prior to Visit 1.
13. Evidence of current alcohol or drug abuse, or history of alcohol or drug abuse within 2 years of Visit 1, based on subject history and physical examination and according to the investigator's judgment.
14. Any other severe medical condition, including severe depression, or any other severe mood disorder, that in the opinion of the investigator may affect efficacy or safety assessments or may compromise the subject's safety during trial participation.
15. Women who are pregnant or breastfeeding.
16. Elevated aspartate aminotransferase or alanine aminotransferase greater than 2-fold upper limit of normal, based on central safety laboratory data obtained at Visit 1, or current evidence of chronic liver disease. Safety laboratory testing may be repeated prior to Visit 2, and subjects will be allowed in the trial if results of 2 consecutive tests, at least 3 days apart, are less than or equal to 2-fold upper limit of normal.
17. Participation in another investigational drug trial within 3 months prior to Visit 1, or any previous trial involving neridronic acid.
18. Subject is engaged in litigation related to their disability from CRPS in which monetary gain or loss (or other compensation) may affect their objective participation in the trial.
19. Subjects taking forbidden concomitant medications/therapies or not being able to follow the rules of use of concomitant treatment (see Section 1.4.2).

20. Subjects incapable of giving informed consent.

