  - Serum calcium or magnesium outside of the central laboratory's reference range, despite appropriate supplementation between Visit 10 and Visit 11, based on the last central safety laboratory data obtained prior to Visit 11. One repeat laboratory test is allowed.
  - Vitamin D deficiency prior to IMP re-allocation, defined as a 25(OH)D level less than 30 ng/mL (75 nmol/L), based on the last central safety laboratory data obtained prior to Visit 11, i.e., inability to normalize 25(OH)D levels to at least 30 ng/mL (75 nmol/L) despite appropriate supplementation between Visit 10 and Visit 11. Two repeat laboratory tests are allowed (with a minimum interval of 3 days).

- Elevated aspartate aminotransferase or alanine aminotransferase greater than 2-fold upper limit of normal, based on central safety laboratory data obtained at Visit 10, or current evidence of chronic liver disease. A single repeat laboratory test is allowed.
- No other criterion for trial and/or IMP discontinuation is met.

The subjects and investigators will stay blinded to the treatment that the subject received in Treatment Period A.

If, at Visit 11, the criteria to continue into Treatment Period B are not met, the subjects will not receive any further IMP infusion and will continue with the follow-up visits Visit 16 and Visit 17. Subjects can only start Treatment Period B at Visit 11.

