## **9.2 Inclusion/exclusion criteria**

The trial population must comply with the inclusion/exclusion criteria given in Section 1.3.

Subjects will only receive IMP if documentation is available showing that they comply with all of these criteria.

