### 9.3.2 Subject discontinuation from the IMP

Discontinuation of IMP applies only to Treatment Period A or Treatment Period B. Subjects who are discontinued from IMP should not be discontinued from the trial except for reasons indicated in [Table 1](#). Subjects who are discontinued from IMP should be encouraged to remain in the trial for their own safety and for the integrity of the trial.

Subjects must be evaluated prior to each infusion of IMP. The investigator must permanently or temporarily discontinue treatment with IMP for any reasons listed in [Table 2](#). The investigator may decide to temporarily discontinue a subject from receiving IMP for other reasons (e.g., if further assessments may be helpful to assure safety of the subject). The investigator may also choose to permanently discontinue a subject from treatment if they believe that continued exposure of the subject to neridronic acid may pose an undue risk to the subject, e.g., due to particular adverse events or due to deterioration in the subject's health for reasons related or unrelated to the treatment.

In situations where treatment is temporarily discontinued, Treatment Period A or Treatment Period B may be extended to a maximum of 21 days (for details, see footnote b) in [Section 1.6.1](#) and [Section 1.6.2](#)).

Table 2: Reasons for permanent and temporary discontinuation of subjects from IMP

Reason	Discontinuation from IMP	
	Permanent	Temporary
Symptomatic hypocalcemia.		X
Serum calcium <7.8 mg/dL (<1.95 mmol/L). The subject may resume treatment following investigator assessment and a repeat serum calcium value above this limit (albumin-corrected serum calcium should be considered if serum albumin is below 3.5 g/dL).		X
Clinical signs of dehydration (e.g., dizziness, palpitations, confusion).		X
Test results suggestive of a possible change in renal function:		

 
• A persistent <math>\geq 25\%</math> decrease in the eGFR from the last value observed prior to the first IMP administration, based on repeated central laboratory results from blood samples obtained at least 1 week apart a.
 
	X	

 
• A <math>\geq 25\%</math> decrease in the eGFR from the last value observed prior to the first IMP administration. If a repeated measurement of eGFR is within 75% or more of the respective value, the subject may resume treatment a.
 
		X

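### Section 8.2 says subjects with known bone-mineralization defects or adynamic bone disease are excluded, but no criterion in Section 1.3.2 does this

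*Protocol*

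**What the plan says.** Section 8.2, under Other effects on bone, describes the benefit/risk balance of bisphosphonates in low-turnover bone conditions as unclear, giving renal osteodystrophy and other adynamic bone disease as examples. It then states that, beyond stage 4 and 5 chronic kidney disease, "subjects with known defects in bone mineralization or adynamic bone disease are excluded from the trial".

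Section 9.2 identifies the list that governs entry: "The trial population must comply with the inclusion/exclusion criteria given in Section 1.3". It ties dosing to that list: "Subjects will only receive IMP if documentation is available showing that they comply with all of these criteria". Section 10.3 likewise allocates subjects who meet all inclusion criteria and none of the exclusion criteria.

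Section 1.3.2 holds 20 numbered exclusions. Those nearest to the subject are criterion 1 (eGFR below 30 mL/min/1.73 m² or urinary albumin to creatinine ratio above 150 mg/g), criterion 2 (calcium or magnesium out of range, or "a history of hypocalcemia or a metabolic disorder anticipated to increase risk for hypocalcemia"), criterion 3 (25(OH)D below 30 ng/mL), criterion 6 (earlier bone-active drugs) and criterion 14, which begins "Any other severe medical condition, including severe depression, or any other severe mood disorder, that in the opinion of the investigator".

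**The concern.** The benefit/risk section reports a categorical safeguard, and the list that releases study drug does not contain it. The kidney half of the Section 8.2 sentence has its criterion; the bone half has none. An ethics committee or regulator reading Section 8.2 would take the protection to be in force, while a site working through Section 1.3 would not be prompted to look for the condition. At stake is the safety of a small group for whom the protocol itself calls the benefit/risk balance unclear. No efficacy result is involved.

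**Working it through.** No arithmetic applies, and the plan gives no figure to reproduce. The check sets the Section 8.2 statement against each place where it could be implemented.

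1. **Inclusion criteria (1.3.1).** 0 of 7 mention the condition.

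2. **Exclusion criteria (1.3.2).** 0 of 20 name a mineralization defect, adynamic bone disease, renal osteodystrophy or low bone turnover. Four give partial or discretionary cover:
   - Criterion 1 removes severe renal impairment only. Section 8.2 presents the bone exclusion as additional to this, so criterion 1 cannot be what implements it. Sections 1.4.1 and 10.2 deliberately treat subjects with eGFR 30 to below 60 at a reduced dose.
   - Criterion 2 acts on calcium, magnesium and the risk of hypocalcemia.
   - Criterion 3 acts on a laboratory level that may be repleted and retested up to 4 times.
   - Criterion 14 needs a severe condition and the investigator's opinion.

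   Criterion 6 lists drugs rather than diseases. Parathyroid hormone is measured at the Enrollment Visit (12.4.5), but no eligibility threshold is attached to it.

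3. **Other exclusions described in Section 8.2.** Severe renal impairment maps to criterion 1, calcium and magnesium to 2, vitamin D to 3, QT risk and potassium to 4, and pregnancy to 15. Against these, the bone exclusion stands out as having no counterpart.

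4. **A subject who passes.** Take eGFR 30 to below 60; albumin to creatinine ratio not above 150 mg/g; calcium and magnesium in range; 25(OH)D at least 30 ng/mL; no hypocalcemia history and no metabolic disorder judged to raise that risk; no earlier drug caught by criterion 6; and known renal osteodystrophy not judged severe. If the remaining criteria are also satisfied, this subject clears Section 1.3, although Section 8.2 calls such subjects excluded.

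5. **Treatment Period B (1.3.3).** There are 8 listed exclusions: renal, QTcF/cardiac, torsades drugs, forbidden medication, dental, calcium/magnesium, vitamin D and liver. None names the condition. The closing clause, "No other criterion for trial and/or IMP discontinuation is met", leads to Tables 1 and 2, which do not name it either.

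Two smaller wording slips were confirmed alongside:
- **Table 2, persistent eGFR below 30.** The row asks for urine samples, but eGFR comes from the creatinine equation given with the clinical chemistry panel (12.4.5), and the parallel row for a decrease of 25% or more asks for blood. The temporary row already suspends dosing, so only confirmation of the permanent stop is affected.
- **ECG reader.** Section 12.4.4 gives exclusion decisions to the investigator's initial evaluation, whereas criterion 4 and Section 1.3.3 assign the Visit 1 and Visit 10 QTcF exclusions to the central reading.

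**The case against.** The best reply is that the gap is mostly formal. Section 8.2 is part of a protocol that principal investigators sign, criterion 14 lets them exclude on safety grounds, and criteria 1 to 3 remove many subjects in whom such bone disease would be found. An investigator might also read renal osteodystrophy into the metabolic-disorder wording of criterion 2. After entry, Section 9.3.2 allows study drug to be stopped where "continued exposure of the subject to neridronic acid may pose an undue risk to the subject". All of this narrows the gap. None of it turns a categorical exclusion into a listed check.

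A second reply is that the conflict does not show which side is wrong. Section 8.2 is not fully in step with Section 1.3 elsewhere: it allows one retest of calcium or magnesium, while criterion 2 allows two. That is fair, and the sponsor must decide. But deleting the sentence would remove a protection that the sponsor has stated.

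Three stronger readings are tempting and not supported:
- A reader might infer that such subjects will be dosed routinely. The protocol gives no count, and the statement in Section 8.2 may itself keep them out.
- A reader might size the hazard by comparing the 400 mg course with the evidence that "no histomorphometric evidence of osteomalacia was reported at doses up to neridronic acid 250 mg". The section does not say whether 250 mg was a single or a cumulative dose, the comparison concerns every treated subject, and an added exclusion would not change it.
- A reader might call the silence of Section 1.3.3 a second contradiction. Section 8.2 states an exclusion from the trial, which is an entry rule, and 1.3.3 repeats only some of the entry exclusions.

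**Conclusion.** The contradiction between Section 8.2 and Section 1.3.2 is real and rests on current protocol text. The stated exclusion appears in 0 of 20 criteria, with 4 of 20 giving partial or discretionary cover. It deserves correction because it is a safety safeguard and eligibility belongs in the protocol, not in an analysis plan. How many subjects it touches is unknown and probably small. The conclusion assumes that the sponsor meant what Section 8.2 says and that sites release study drug on the Section 1.3 list, as Section 9.2 directs. There is no consequence for the endpoint, power or type I error.

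**What to change.** Add one numbered exclusion to Section 1.3.2: known defect in bone mineralization or adynamic bone disease, assessed from the medical history taken at Visit 1 (Section 12.2.3). The cost is amendment wording and perhaps a few more ineligible subjects; no procedure is added.

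A matching line in Section 1.3.3 is optional. If it is wanted for diagnoses made after entry, it needs its own check at Visit 11, because medical history is scheduled only at Visit 1.

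Minor wording corrections for the same amendment:
- In the persistent eGFR below 30 row of Table 2, replace urine samples with blood samples.
- In Section 12.4.4, except the Visit 1 and Visit 10 QTcF exclusions that Section 1.3 assigns to the central reading.

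The ocular text also differs: Section 8.2 has an eye examination follow the first signs, while footnote b of Table 2 requires it for persistent or recurrent signs. It may be left alone. If it is reconciled, the examination after first signs should be kept.
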